Active syndromic population surveillance (biweekly) with PCR testing of symptomatic individuals – 12 months	15393 individuals (2108 households) Possible cases reporting any respiratory sign or loss of smell or taste, with or without fever, selected for PCR testing. Initially, before widespread community transmission, pooled testing of possible cases; when >50 confirmed cases per week, switch to PCR testing of 1 in 10 possible cases (systematic selection - every 10th possible case)	
 
● COVID-19 disease incidence rate (symptomatic infections per person-month)
 
● COVID-19 related hospitalisation rate
 
● Case (disease) fatality risk (%)
 
● Risk factors for severe outcome/hospitalization
 
● Basic reproduction number
 
● Effective reproduction number
 
● Serial interval
 
● Proportion uptake of measures to prevent infection; barrier uptake
 
● Effectiveness of interventions
 

		
 
• COVID-19 incidence density maps
 
• COVID-19 likelihood ratios of clinical signs
 
• Brand-specific vaccine effectiveness against confirmed COVID-19 (disease)
 

Age-stratified sero-survey at 0, 3, 6, 12 months	2400 individuals/dried blood spot samples per round (800 per age group <18yo, 18-50 yo, >50yo) An age stratified sample of individuals will be selected (simple random sample in each age group)	
 
• SARS-CoV-2 infection annual attack rate (%)
 
• Infection fatality risk
 
• Proportion asymptomatic infections, by age group
 
• Risk factors for infection
 
• Association between antibody titers and reinfection
 
• Brand-specific total vaccine effectiveness against SARS-CoV-2 seroconversion
 
• Overall vaccine effectiveness against SARS-CoV-2 seroconversion
 

Repeated social mixing survey	the same 2400 individuals selected for the sero-survey (800 per age group <18yo, 18-50 yo, >50yo)	
 
• correlation between number of contacts, intensity of contacts and attack rate
 
• correlation between uptake of control measures and attack rate
 
• social contact matrices to be used to parametrize dynamic transmission models
 

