## 4. Participants, Population & Selection

### 4.1 Setting

Polana Caniço, peri-urban Maputo, Mozambique: a health- and demographic surveillance system (HDSS) covering a population of 15,393, in the catchment area of the Polana Caniço General Hospital (PCGH), one out of two COVID-19 referral facilities in Maputo.

The population in peri-urban Polana Caniço is relatively representative of the increasingly urban population in Southern Africa, having young and mobile inhabitants. Moreover, the population suffers increasingly from non-communicable diseases, and prevalence of HIV and active tuberculosis is presumed to be important. Research gaps on COVID-19 transmission dynamics include whether the reproduction number could be different in such different (eg. younger) population. Also, the potential association between (uncontrolled) HIV infection or (active) tuberculosis and COVID-19 infection and severe disease, needs to be elucidated.

The Polana Caniço-HDSS has been established since 2017. In total, as of time of writing, 2108 households (defined as residents of the same building, sharing a cooking area) have been enrolled in the HDSS. All members residing in the household for at least 3 months (infants, children, adults, elderly) are enrolled in the HDSS. Surveillance rounds are currently carried out six-monthly. Demographic and health indicators collected in each surveillance round include but are not limited to: fertility/birth rate, mortality/cause of death, migration, disease cases, trauma and violence, socioeconomic status, water and sanitation facilities, risk factors for the acquisition of chronic diseases, women's health and family planning, immunization, risk behaviours and cultural practices related to the transmission of STI (including HIV and syphilis). Testing for HIV and syphilis is planned to be added as part of the surveillance rounds, from October 2020 onwards. Data on births, deaths, internal and external migration, pregnancies and their outcomes, and any other relevant events from a demographic perspective, are continuously reported by community key informants and confirmed through home visits.

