In case that the head of the household or his representative is not available by phone (number disconnected or unreachable or without contact details), an interviewer will perform a visit for this

household. In addition to calls, home visits to households will be performed every three months to collect data in person.

Any adolescent or adult able to self-administer a nasal swab will be asked to do so, at the participants home. For children or adults not capable of self-swabbing, the trained interviewer will put on personal protective equipment and collect a nasal swab. Preferentially, if confidentiality allows, the swab will be taken outside. Alternatively in a room without other household members. A 'Possible case report form', based on the WHO case report form, will be completed, recording symptoms, recent risk exposure, and potential contact with COVID-19 cases.

If in between household visits, a household member can inform the study team by phone when he/she develops any sign that could be indicative of COVID-19, so that a trained interviewer will be dispatched to assess whether the signs qualify for a possible case, complete the 'Possible case report form', and collect a nasal swab (again by self-swabbing if possible) at the possible cases' home.

If during household visits or through phone call, the interviewer is notified that a participating household member has been admitted to a healthcare facility or presented to the COVID-19 clinical management centre at Polana Caniço General Hospital, the participant will be actively approached, and if applicable, a 'Possible case report form' filled. If SARS-CoV-2 PCR testing has been done already, results will be requested and entered in a 'Possible case lab request and result form'. If no SARS-CoV-2 PCR testing has been done yet, a nasal swab will be collected if indicated, following the same procedure as above.

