## 7.2 Sample size and power

Assuming a 40% annual attack rate, 50% symptomatic infections (cases), 2% overall case fatality risk, of which 90% are identified by the active population surveillance, 2790 COVID-19 cases and 56 deaths will be identified through the study period. The average incidence rate of the HDSS population would then be 1.50 cases per 100 person months with lower and upper 95% confidence interval limits 1.45 and 1.56. The overall case fatality risk would have as lower and upper 95% confidence interval limits at 1.53 and 2.58%.

To determine the infection attack rate from a simple random population sample of three age strata (comparable in size), with +/-3% confidence limits, 95% confidence interval, assuming the attack rate may reach 40% towards the end of the study period, samples from 800 individuals per age stratum per round will need to be collected.

Assuming the household secondary attack rate to be close to 17% (Fung et al, Clin Infect Dis, 2020) and a median household size of 7.3 (based on HDSS data), a 5% confidence limit and a design effect of 3, 642 household members will need to be enrolled, or 100 households. The WHO also recommended to include 100 households in household transmission investigations.

Assuming 20% vaccination coverage among the 2400 sero-survey participants, 5% of sero-conversion over 3 months and 10% of seroconversion over 6 months, a 95% two-sided confidence interval and an anticipated crude total vaccine effectiveness of 50%, there will be 66% power to observe this effect after 3 months and 97% power after 6 months.

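### Above 50 confirmed cases a week the PCR testing fraction differs by entry route and no analysis weights for it, so an unweighted case fatality risk would probably be biased upward

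*Combined protocol and SAP*

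**What the plan says.** - **Testing rule (Section 2, Table 1; repeated in Section 5.1, Table 4).** At first all possible cases are tested, in pools. Above 50 confirmed cases a week the study will "switch to PCR testing of 1 in 10 possible cases (systematic selection - every 10th possible case". No route is exempted, and there is no rule for returning to full testing.
- **Facility route (Section 5.1).** For a participant admitted to a facility or seen at the COVID-19 centre, "If SARS-CoV-2 PCR testing has been done already, results will be requested and entered". A patient not yet tested is swabbed where indicated, using the field procedure. Whether the 1-in-10 rule covers either group is not said.
- **Household investigations (Sections 4.2 and 5.1).** For up to 100 index cases, contacts are swabbed at baseline and at day 28 whatever their symptoms, and symptomatic contacts are to be tested when symptoms appear.
- **Outcomes (Section 5.1; Section 2, Table 1).** Follow-up at days 28 and 56 covers confirmed cases only. Table 1 lists case fatality risk, a hospitalisation rate and risk factors for severe outcome under the surveillance.
- **Analysis (Section 7.1).** Adjustment is planned for clustering and for PCR sensitivity by delay. Nothing is planned for testing fraction or route.
- **Precision (Section 7.2).** "Assuming a 40% annual attack rate, 50% symptomatic infections (cases), 2% overall case fatality risk", "of which 90% are identified by the active population surveillance", leading to "2790 COVID-19 cases and 56 deaths will be identified through the study period". "The overall case fatality risk would have as lower and upper 95% confidence interval limits at 1.53 and 2.58" per cent.

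**The concern.** Case fatality risk is deaths among confirmed cases divided by confirmed cases. After the switch, a mild case found at home has a 1 in 10 chance of entering that denominator. A case tested at a facility can enter without passing through the 1-in-10 step, and patients who reach a facility are likely to be sicker on average. Pooling the two without weights changes the severity mix of the sample as well as its size.

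The estimate would also jump when the testing rule changes. Section 10.2 plans to present case fatality to health authorities after 3, 6 and 12 months, and such a jump could be read as a change in the disease. Multiplying every confirmed case by ten would not repair it, because that would also multiply facility cases that were never sampled at 1 in 10.

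**Working it through.** **1. The plan's own figures.** Population from Section 4.1: "covering a population of 15,393".

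- Cases = 15,393 × 0.40 × 0.50 × 0.90 = 2,771; deaths = 2% = 55.4. A population of 15,500 gives exactly 2,790 and 55.8. The stated counts are reproduced to within 0.7%.
- 95% interval for 56/2,790: Wilson 1.55% to 2.60%, Clopper-Pearson 1.52% to 2.60%. The stated 1.53% to 2.58% agrees closely. It assumes 90% identification all year, with no switch in testing.

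**2. Is the trigger reached?** 2,790/52 = 53.7 a week (2,771/52 = 53.3). An epidemic wave concentrates cases further. For an assumed bell-shaped wave with an SD of 3 to 10 weeks and a permanent switch, about 88% to 97% of cases fall after the switch. Even at SD 10 weeks the peak is about 2,790/(10 × 2.507) = 111 a week.

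**3. Bias of the unweighted case fatality risk.** Let f be the share of cases arising under 1-in-10 testing, h the share of cases that are facility-tested, d the share of deaths never facility-tested, and pF the capture probability at a facility. The documents give none of these.

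Ratio to truth = [(1−f) + f(pF(1−d) + 0.1d)] / [(1−f) + f(pF·h + 0.1(1−h))]

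With pF = 1, numerator minus denominator is 0.9f(1−d−h). The bias is therefore upward whenever deaths are more often facility-tested than cases in general (1−d > h).

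As a proxy for h, the national severity mix in the Section 1.2 box gives (6+1)/44 = 15.9% of symptomatic cases moderate or severe. Using it here is an assumption. With f = 1, pF = 1 and a true value of 2%:

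| h | denominator | all deaths facility-tested (d = 0) | half of deaths not (d = 0.5) |
|---|---|---|---|
| 5% | 0.145 | 6.9× (13.8%) | 3.8× |
| 10% | 0.190 | 5.3× (10.5%) | 2.9× |
| 15.9% | 0.243 | 4.1× (8.2%) | 2.3× |
| 30% | 0.370 | 2.7× (5.4%) | 1.5× |
| 50% | 0.550 | 1.8× (3.6%) | 1.0× |

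- Facility capture of 90% instead of 100% changes 4.1× to 4.0×.
- Whole study, permanent switch, waves as in step 2, d = 0: 3.0× to 3.7× at h = 15.9%; 4.0× to 5.8× at h = 5%.
- Only half of cases after the switch, h = 15.9%, d = 0: 1/(0.5 + 0.5 × 0.243) = 1.6×.
- Half after the switch, h = 20%, d = 0.5: 0.775/0.64 = 1.2×, or 2.4%, which lies inside the stated interval.

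**4. Household route.** The formula leaves it out. On Section 7.2's figures, 642 contacts × 17% × 50% symptomatic = 55 cases. If all arose after the switch and none was facility-tested, they would add 0.9 × 55 = 49 confirmed cases to 2,790 × 0.243 = 678. The case fatality risk would then be 55.8/727 = 7.7% instead of 8.2%.

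**5. If 1 in 10 applies to every route (f = 1).** 2,790/10 = 279 cases and 55.8/10 = 5.6, say 6, deaths. There is no bias, but the Wilson interval is 1.0% to 4.6%.

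**6. Severity risk ratios among confirmed cases.** Assume true severity risks of 10% and 5% (ratio 2.0), with non-severe cases sampled at 0.1. The observed risks are 0.10/0.19 = 52.6% and 0.05/0.145 = 34.5%, a ratio of 1.53. The odds ratio is unchanged: (0.10/0.90)/(0.05/0.95) = (0.10/0.09)/(0.05/0.095) = 2.11.

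**The case against.** The strongest reply is that the documents do not establish unequal capture as a fact. Nothing exempts facility patients from the 1-in-10 rule, and on a uniform reading there is no bias. Facility capture also depends on the study team being notified or on an alert to which the patient agrees (Sections 3 and 5.1). The facility route includes outpatients as well as admissions, so facility-tested does not mean severe, and a large facility share shrinks the effect. Case fatality risk is not among the bolded primary outcomes in Table 1. The sampling fraction is known, so the estimate can be corrected if the route is available.

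Much of this stands. A reader might infer that severe cases enter with near certainty and that case fatality is inflated several-fold as a settled result. The first is only an inference, and the second depends on facility shares of cases and deaths that the documents do not give. A reader might also infer that hospitalisation is overstated. The listed outcome is a rate; per person-time it has no sampled case denominator, so this mechanism does not inflate it. Nor are severity risk ratios pushed upward: they move toward 1.

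What the reply does not remove is that the plan leaves the rule by route unstated, provides no weight, and gives a precision figure that ignores a switch its own case count would reach.

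**Conclusion.** The point holds, as a gap in the sampling rule and analysis that would probably bias an unweighted case fatality risk upward. The documents do not fix the size. A true 2% reads as about 8% above the trigger if 16% of cases and all deaths are facility-tested. Over the scenarios tabulated the factor runs from about 1 to 7, and it reaches 1 when half of cases are facility-tested and half of deaths are not. Direction rests on deaths being more often facility-tested than cases overall, which is plausible but unstated.

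Risk ratios for severity restricted to confirmed cases would be attenuated. The population hospitalisation rate is not inflated by this route. With the 1-in-10 rule in force, the interval in Section 7.2 does not reflect the testing rule on either reading: unequal capture shifts the estimate, and uniform capture widens the interval to about 1.0% to 4.6% if the rule applies throughout.

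**What to change.** 1. State in Table 1, Table 4 and Section 5.1 which entry routes the 1-in-10 rule covers, and when full testing resumes.
2. Record for each confirmed case the route of confirmation (field, facility, household investigation) and the testing period. The forms are not in the documents, so this may already be partly captured; Section 4.2 lists four entry points.
3. Estimate case fatality risk with inverse-testing-probability weights. If facility results stay outside the 1-in-10 rule, use weight 10 only for cases confirmed through 1-in-10 field sampling, and weight 1 for facility-tested, household-investigation and full-testing-period cases. Giving household contacts weight 10 would be a new error. Say in advance how to weight a field-sampled case who later reaches a facility, since that case had two ways in.
4. For severity risk factors among confirmed cases, use weighted models or logistic odds ratios. The odds ratio is protected only where selection depends on severity alone; otherwise weight.
5. Restate the case count and case fatality interval in Section 7.2 under the testing rule.

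The cost is some added analysis, at most a small change to the forms, and a wider stated interval. Route may be hard to reconstruct later, so it should be recorded from the start.

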## 1.2 Rationale

It is recognized that SARS-CoV-2 will transmit differently in African settings, and that risk factors for infection and mild or severe disease may be different to higher income settings. Understanding transmission and identifying at-risk populations is urgent for African countries, who need to target scarce resources as effectively as possible to interrupt transmission and protect vulnerable risk groups.

Box. The epidemiological situation in Mozambique on 29/09/2020.

The SARS-CoV-2 outbreak is still accelerating in Mozambique, as indicated by both the trend in the number of reported cases and the positivity rate. 7983 SARS-CoV-2 infected cases were reported, including 295 imported cases, and 58 deaths. Since the start of the outbreak, 134,011 suspected cases have been tested. In September 2020, consistently more than half of new cases were reported in Maputo City. In Maputo City a total of 3,427 cases and 38 deaths have been reported. The average number of new daily cases reported went from 47 in the first week of September, to 97 in the week up to 26/09. A sero-prevalence survey undertaken in the last two weeks of August 2020, found an overall seroprevalence of 3.8% in Mauto city, with only slight variation between age groups (range 3.0% in 35-59 year olds to 4.5% in  $\geq 60$  year olds). Nevertheless, the latter age group accounts for the majority of hospitalisations. Of all cases reported in Mozambique, 56% were asymptomatic, 37% have a mild symptomatology, 6% moderate symptomatology and 1% a severe symptomatology. 42% of the infected individuals are female.

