An **age-stratified random sample** of that population will be selected for the **repeated sero- and social mixing survey**. By age stratum (0-17 years; 18-50 years; >50 years) we randomly select 800 individuals (simple random sample per age stratum; 2400 in total) from the Polana Caniço HDSS population (regardless of infection or disease status or history), from whom during home visits dried blood spots will repeatedly be collected at 0, 3, 6 and 12 months, vaccination status against COVID-19 will be recorded, and who will be asked to respond to a social mixing questionnaire. A HDSS sampling frame of all individual participants in the HDSS with socio-demographic data and unique identifiers, is available, and will be used to select a simple random sample of individuals by age group.

When a member of a household with no prior widespread transmission (see exclusion criteria) tests SARS-CoV-2 positive, we will revisit the household twice for a household transmission investigation: as soon as possible after the result of the household index case (baseline), and once again one month after symptom onset of the household index case. An initial contact report form will be filled in as soon as possible, ideally within 24 hours, after laboratory confirmation of the primary case in the household. Respiratory and dried blood spot samples will be collected of everyone considered resident (as defined by the HDSS) in the household and who has been in contact with the SARS-CoV-2 positive individual, regardless of age and presence or absence of symptoms. Respiratory samples will be analysed by RT-PCR for SARS-CoV-2 to assess presence of virus and viral load. The dried blood spots for serology on the Luminex assay. Data will be collected on household exposures of contacts and vaccine receipt. Symptomatic household contacts will be tested whenever symptoms appear, as part of the population-based surveillance. This is planned for upto 100 household index cases.

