The repeated sero-survey, collecting dried blood spots through a finger prick, will be added to the biweekly household visits at 3, 6 and 12 months after COVID-19 local transmission is confirmed. During four other biweekly household visits, the participants selected for the sero-survey will also be interviewed on contact and mobility patterns during the previous day, and uptake of COVID-19 control measures, using the 'Social mixing questionnaire'. Its timing will depend on the stage of the outbreak:

1. shortly after the baseline interview (second visit),
2. when local transmission is well established and the number of new cases is increasing,
3. a month after an initial peak, when the number of new cases is decreasing,
4. during the final study visit.

Table 4 . Forms completed during each study activity

Planned activities	Sample size	Research form
Baseline household visit	15393 individuals (2108 households)	
 
· Informed consent form for population-based COVID-19 surveillance (with household head)
 
· Informed consent form for serial sero-survey (with selected individual)
 
· Baseline household visit form
 

Active syndromic population surveillance	15393 individuals (2108 households) visited every 2 weeks	
 
· Household follow-up visit form
 

Swabbing & PCR testing of symptomatic individuals	possible cases from the surveillance population; initially pooled testing of possible cases; when >50 confirmed cases per week, switch to PCR testing of 1 in 10 suspected cases	
 
· Possible case report form
 
· Possible case lab request and result form
 

Follow-up of PCR confirmed cases at day 28 and day 56 past symptom onset	PCR confirmed cases from the surveillance population	
 
· Confirmed case follow-up form
 

Age-stratified sero-survey at 0, 3, 6, 12 months	2400 individuals/serum samples per round (800 per age group <18yo, 18-50 yo, >50yo NOTE: this is budget dependent, pending cost of	
 
· Sero-survey form
 
· Sero-survey lab request and result form
 

	assay, might be decreased to 1600, spread over two age strata)	
Social mixing survey	the same 2400 individuals selected for the sero-survey; during different HH visits than sero-survey visits	· Social mixing questionnaire

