## 7. Statistical Analyses

### 7.1 Methods

All estimated transmission or clinical outcome indicators will be adjusted for the design effect, related to the selection of HDSS enumeration areas (clusters) within the source populations. Intraclass correlation coefficients can be deducted from previous studies in the HDSS. The results of the sero-survey and social mixing survey will additionally be adjusted for age-stratified sampling.

We will calculate a incidence rate of COVID-19 disease throughout one year, adjusting for the sensitivity of SARS-CoV-2 RT-PCR on nasal swabs by delay between symptom onset and testing. Using the longitudinal sero-survey data, determining the proportion of asymptomatics, we will be able to adjust the clinical incidence rate to a SARS-CoV-2 infection incidence rate, and determine the SARS-CoV-2 infection annual attack rate and the infection fatality risk by age group.

We will undertake three risk factor analyses: of SARS-CoV-2 infection, of COVID-19 disease (symptomatic infection), and of COVID-19 hospitalisation and death (severe disease). Using negative binomial regression, we will investigate the association with socio-demographic factors, clinical characteristics such as underlying medical conditions, and uptake of preventive measures. We also investigate the association between SARS-CoV-2 infection (from the sero-survey) and recent exposure, contact and mobility patterns (from the social mixing questionnaire).

We will assume everyone will be susceptible initially and basic and effective reproductive numbers ( $R_0$  and  $R_e$ ) will be calculated by the rate of change of incidence over successive serial intervals (time between onset of infection of index and onset of infection of infected).

We will use established methods (Cauchemez et al 2004; te Beest et al 2013) to estimate generation time distribution, ratio of transmissibility between symptomatic and asymptomatic cases, duration of

the infectious period, and the basic reproduction number, from the transmission data collected in households.

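### If assay cost forces the sero-survey down to 1,600, keep all three age strata at about 533 each instead of cutting to two strata

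*Combined protocol and SAP*

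**What the plan says.** Section 4.2 fixes the design: "By age stratum (0-17 years; 18-50 years; >50 years) we randomly select 800 individuals", 2,400 in all. The synopsis and Table 1 give the same three strata and the same 800 per stratum. Section 7.2 takes three strata of similar size, a final attack rate of 40%, 95% confidence and a half-width of 3 points, and concludes that "samples from 800 individuals per age stratum per round will need to be collected".

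Table 1 marks the annual attack rate in bold as the primary outcome of the sero-survey and lists the asymptomatic proportion by age group as a further outcome. Section 7.1 plans to "determine the SARS-CoV-2 infection annual attack rate and the infection fatality risk by age group". It also feeds the age-specific asymptomatic proportion into the household chain-binomial model.

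Only the sero-survey row of Table 4 departs from this. It repeats 2,400, then makes that number conditional on the budget and the price of the assay, and says the sample "might be decreased to 1600, spread over two age strata". The next row of Table 4 keeps the social mixing survey at the same 2,400 people and offers no reduced option. Section 7.2 has no calculation for 1,600.

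**The concern.** Going from three strata to two means either leaving one age group unsampled or merging two groups. The note does not say which, which ages are affected, who decides or when.

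The two routes have different consequences. Dropping a stratum leaves an age group with no serology, and no weighting can restore it. Merging keeps the whole population covered but removes the guaranteed 800 for one planned age group. That weakens the asymptomatic proportion and the infection fatality risk by age group. The saving does not require either loss, because the same number of assays can be spread over the three existing strata.

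**Working it through.** **Inputs.** From section 7.2: attack rate 40%, 95% confidence, target half-width 3 points, 800 per stratum, strata comparable in size; for vaccine effectiveness (VE), 20% coverage, 5% and 10% seroconversion at 3 and 6 months, VE 50%. From Table 4: fallback total 1,600. From the setting: 15,393 residents. Assumptions: equal strata (15,393/3 = 5,131 each) and, under the note, an equal split of 800 + 800.

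**1. The plan's own figure.** n = 1.96² × 0.4 × 0.6 / 0.03² = 1,025 per stratum, or 854 with finite population correction for N = 5,131. So 800 is not reproduced exactly. With 800 the half-width is 1.96 × √(0.24/800) = 3.4 points (3.1 with correction). That is a separate matter; 3.4 is the reference below.

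**2. Note read as dropping a stratum.** The two retained strata keep +/-3.4 points. About 5,131 residents, one third, have no serology. Illustration: if the retained strata are both at 40% and the missing one is truly q, reporting 40% for everyone has bias 0.40 − (0.80 + q)/3.

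| True rate in dropped stratum | Bias in overall rate |
|---|---|
| 20% | +6.7 points |
| 30% | +3.3 points |
| 50% | −3.3 points |

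**3. Note read as merging two strata.** A simple random 800 from two equal groups gives about 400 from each: 1.96 × √(0.24/400) = 4.8 points (4.6 with correction). The documents give no age distribution. If a group were only 15% of the merged stratum (assumed), it would supply 120 people: 1.96 × √(0.24/120) = 8.8 points. The overall rate, weighted 2/3 and 1/3, has half-width 1.96 × √[0.24 × (4/9 + 1/9)/800] = 2.5 points.

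**4. Same 1,600 over three strata.** 1,600/3 ≈ 533. Per stratum: 1.96 × √(0.24/533) = 4.2 points. With correction: 4.16 × √[(5,131 − 533)/5,130] = 3.9. Overall: 1.96 × √(0.24/1,600) = 2.4 points.

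| Allocation | Smallest planned age group | Overall rate |
|---|---|---|
| 3 × 800 | +/-3.4 | +/-2.0 |
| 2 × 800, one dropped | no data | needs extrapolation |
| 2 × 800, two merged | +/-4.8 (equal groups); +/-8.8 (15% share) | +/-2.5 |
| 3 × 533 | +/-4.2 | +/-2.4 |

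The table has no finite population correction and no design effect.

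**5. VE power.** Two-proportion z-test with pooled variance under the null, taking the stated seroconversion as the unvaccinated rate. At 2,400 (480 vaccinated, 1,920 unvaccinated), 3 months: null SE = √[0.045 × 0.955 × (1/480 + 1/1,920)] = 0.01058; alternative SE = √(0.025 × 0.975/480 + 0.05 × 0.95/1,920) = 0.00869; power = Φ[(0.025 − 1.96 × 0.01058)/0.00869] = 69%. The same formula gives 96% at 6 months. The plan states 66% and 97%, so this is close but not exact. At 1,600 (320 and 1,280) it gives 49% and 84%. If the stated rates are overall rates, 1,600 gives 54% and 89%.

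**The case against.** The strongest reply is that this is a contingency, and that the natural reading of the note is a re-cut of the whole population into two strata. The bold outcome in Table 1 is the overall annual attack rate, with no age qualifier. Under a merge it remains estimable with weights, at about +/-2.5 points against +/-2.4 for three strata of 533. Ages are known from the sampling frame, so a merged group can still be reported as a subdomain. The note also keeps 800 per retained stratum, which is the number section 7.2 asks for. All of this stands. It limits the point to age resolution under a merge, and to missing coverage only under a drop.

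Several stronger readings are tempting but not supported:

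- **That the fallback makes the primary outcome non-estimable.** This follows only if a stratum is dropped, which the note does not say.
- **That the over-50 group is the one at risk.** The documents do not say which strata would be merged. The remark in the section 1.2 Box that "the latter age group accounts for the majority of hospitalisations" concerns people aged 60 and over, and the same Box reports only slight variation in seroprevalence by age (3.0% to 4.5%).
- **That section 7.1 depends on three strata and 2,400 people.** It names neither; it speaks only of age groups and age-stratified sampling.
- **That the contact matrix would lose a row.** The trigger is assay cost, the mixing survey needs no assay, and its row in Table 4 stays at 2,400.
- **That two strata cause the loss of VE power.** Power falls because the total falls to 1,600, under either allocation.

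What the reply does not meet is that the note leaves the drop reading open, and that a same-cost allocation removes it.

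**Conclusion.** The note permits a cut that conflicts with the three-stratum design elsewhere and is inferior to an equally cheap alternative. Three strata of about 533 rule out an unsampled age group and guarantee each planned group about +/-4.2 points, where a merge leaves +/-4.8 or worse for the merged groups. Precision of the overall rate is about the same or slightly better. The price is about 0.8 points per stratum relative to 800 (4.2 against 3.4).

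These sizes assume a 40% attack rate, strata of equal size and an equal split of the 1,600, before any design effect. The bias figures for a dropped stratum are illustrations with assumed rates. The VE power at 1,600 is approximate, because the plan's own figures at 2,400 are matched only closely. This is a cheap improvement rather than a flaw in the main plan, and it applies only if the fallback is invoked.

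**What to change.** Replace the Table 4 note with: *If assay cost requires a reduction to 1,600, all three age strata are kept with about 533 each, a random subset of the 800 selected per stratum; the social mixing survey stays at 2,400.*

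Add to section 7.2 that under this fallback:

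- the half-width is about +/-4.2 points per stratum at a 40% attack rate (about 3.9 with finite population correction if strata are about 5,131 each), before any design effect;
- VE power at 1,600 is about 49% at 3 months and 84% at 6 months by a normal approximation that gives 69% and 96% at 2,400, so the stated 66% and 97% do not apply. The sponsor should recompute these with its own method.

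The cost is one sentence in Table 4 and a short addition to section 7.2, with the same 1,600 assays per round. The downside is a half-width about 0.8 points wider per stratum than with 800. The change does not recover the lost VE power; it only makes it explicit.
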